11.0 HUMAN SUBJECT PROTECTION

The investigator(s) accept their responsibilities for protecting the rights and welfare of human research subjects and will permit, with reasonable advance notice and at reasonable times, the designated research monitors to monitor the conduct of the research, as well as to audit source documents to the extent necessary to verify compliance with FDA Good Clinical Practice and the approved protocol.

11.1 Rationale for Subject Selection

11.1.1 Predicted distribution by gender, age and race:

CLL is a rare neoplasm that comprises a substantial proportion of all leukemia in middle-aged persons and is the most common type among elderly persons in western populations. Epidemiologic studies suggest that distribution by gender will be 66% males and 33% females.¹³ This trend appears to be lost with age. CLL is more common in Caucasian and African-American but rare in Hispanics and very rare in the Asian population. This study will be open to all patients who fit the inclusion criteria and provide informed consent to protocol participation. We would predict that distribution should be comparable to that seen on the NHLBI Hematology Branch screening protocol as follows:

- by gender: 33% females; 66% males
- by age: ages 23-79, median 60
- by race: 2% Asian, 11% Black, 8% Hispanic, 79% White

11.1.2 Special Populations:

Justification for inclusion of previously untreated CLL: Ibrutinib is FDA-approved for the treatment of relapsed/refractory CLL and is therefore available outside of clinical trials. Furthermore, a substantial proportion of relapsed/refractory CLL is refractory to fludarabine-based regimens, which is typically given as a first-line drug. Thus, the combination of ibrutinib and short-course fludarabine is likely more effective in previously untreated CLL than in relapsed/refractory CLL.

Justification for exclusion of children: CLL is uncommon in patients less than 45 years of age and is virtually unknown in patients less than 20 years of age. At the time of diagnosis, more than 95% of patients are 45 years old and above.¹⁴ CLL may also be, biologically, a different disease in children. Ibrutinib has not been studied in human subjects under 18 years of age. For these reasons, individuals < 18 years old have been excluded from protocol participation.

Justification for Exclusion of pregnant women: There are no clinical studies that were done on pregnant women, and it is unknown whether ibrutinib or its metabolites are excreted in human milk. In addition, it is highly unlikely that a woman of pre-menopausal age will present with CLL or SLL at the Clinical Center. CLL/SLL is a malignancy of B cells that predominantly affects the elderly population. Diagnosis is typically made in adults over the age of 50 and more than half of the people with CLL/SLL are over the age of 70.

Justification for Exclusion of patients with impaired hepatic or renal function: No specific clinical studies have been conducted to date in patients with impaired hepatic or renal function. To minimize risks, patients enrolled must have AST and ALT levels $< 3.0 \times$ the institutional upper limit of normal (ULN) and a creatinine level $\leq 2.0 \times$ the institutional ULN.

Justification for Exclusion of Cognitively Impaired Subjects: Cognitively impaired and institutionalized persons will not participate in this study. Subjects must be able to provide informed consent, and understand and comply with the treatment plan and follow-up.

Inclusion of NIH Staff (At NIH CC only): NIH staff may voluntarily participate in this protocol. Recruitment, enrollment and compensation of NIH staff will be consistent with the Guidelines for the Inclusion of Staff in NIH Intramural Research Studies (April 2016) (HRPP SOP 14F, Appendix A; also Appendix C of this protocol) and NIH Policy Manual Chapter 2300-630-3 “Leave Policy for NIH Employees Participating in NIH Medical Research Studies” (HRPP SOP 14F, Appendix B).

Recruitment: The study will be listed on the clinicaltrials.gov, Clinical Center research studies, and the National Heart, Lung and Blood Institute patient recruitment websites. If recruitment goals are not met, a recruitment plan will be developed by the Clinical Center Office of Patient Recruitment.

Payment for participation: \$0 – Subjects will not be compensated for their participation in this study. There is no payment for the blood samples obtained for research.

Reimbursement for protocol participation travel, food, and lodging will be consistent with NIH guidelines.

Competition with other Branch protocols: This trial is the only active treatment protocol for treatment-naïve CLL/SLL patients without deletion 17p. There will be little to no competition with existing branch protocols.

11.2 Risks and discomforts

11.2.1 Risks related to Ibrutinib

Bleeding-related events

There have been reports of hemorrhagic events in subjects treated with ibrutinib both with and without thrombocytopenia. These include primarily minor hemorrhagic events such as contusion, epistaxis, and petechiae; and major hemorrhagic events, some fatal, including gastrointestinal bleeding, intracranial hemorrhage and hematuria. Use of ibrutinib in subjects requiring other anticoagulants or medications that inhibit platelet function may increase the risk of bleeding. Subjects with congenital bleeding diathesis have not been studied. See Section 6.2.4 for guidance on concomitant use of anticoagulants, antiplatelet therapy and/or supplements. See Section 5.5 for guidance on ibrutinib management with surgeries or procedures.

Cardiac Arrhythmias

Atrial fibrillation and atrial flutter, and cases of ventricular tachyarrhythmia including some fatal events, have been reported in subjects treated with ibrutinib, particularly in subjects with cardiac risk factors, hypertension, acute infections, and a previous history of cardiac arrhythmia. Subjects who develop arrhythmic symptoms (eg, palpitations, lightheadedness) or new onset of dyspnea should be evaluated clinically, and if indicated, have an ECG performed. For cardiac arrhythmia which persists, consider the risks and benefits of ibrutinib treatment and follow the protocol dose modification guidelines (see Section 5.4).

Cytopenias

Treatment-emergent Grade 3 or 4 cytopenias (neutropenia, thrombocytopenia, and anemia) were reported in subjects treated with ibrutinib. Subjects should be monitored for fever, weakness, or easy bruising and/or bleeding.

Diarrhea

Diarrhea is the most frequently reported non-hematologic AE with ibrutinib monotherapy and combination therapy. Other frequently reported gastrointestinal events include nausea, vomiting, and constipation. These events are rarely severe. Should symptoms be severe or prolonged follow the protocol dose modification guidelines (see Section 5.4).

Infections

Infections (including sepsis, bacterial, viral, or fungal infections) were observed in subjects treated with ibrutinib therapy. Some of these reported infections have been associated with hospitalization and death. Consider prophylaxis according to standard of care in subjects who are at increased risk for opportunistic infections. Although causality has not been established, cases of progressive multifocal leukoencephalopathy (PML) and hepatitis B reactivation and pneumocystis pneumonia have occurred in patients treated with ibrutinib. Subjects should be monitored for signs and symptoms (fever, chills, weakness, confusion, vomiting and jaundice) and appropriate therapy should be instituted as indicated.

Tumor Lysis Syndrome (TLS)

There have been reports of tumor lysis syndrome (TLS) events in subjects treated with single-agent ibrutinib or in combination with chemotherapy. Subjects at risk of tumor lysis syndrome are those with comorbidities and/or risk factors such as high tumor burden prior to treatment, increased uric acid (hyperuricemia), elevated lactate dehydrogenase (LDH), bulky disease at baseline, and pre-existing kidney abnormalities.

Liver Failure

Rare cases of liver failure have been reported in patients treated with ibrutinib.

Non-Melanoma Skin Cancer

Non-melanoma skin cancers have occurred in patients treated with ibrutinib. Monitor patients for the appearance of non-melanoma skin cancer.

Rash

Rash has been commonly reported in subjects treated with either single agent ibrutinib or in combination with chemotherapy. Most rashes were mild to moderate in severity. Isolated cases of severe cutaneous adverse reactions (SCARs) including Stevens-Johnson syndrome (SJS) have been reported in subjects treated with ibrutinib. Subjects should be closely monitored for signs and symptoms suggestive of SCAR including SJS. Subjects receiving ibrutinib should be observed closely for rashes and treated symptomatically, including interruption of the suspected agent as appropriate. In addition, hypersensitivity-related events including erythema, urticaria, and angioedema have been reported.

Interstitial lung disease

Cases of interstitial lung disease (ILD) have been reported in subjects treated with ibrutinib. Subjects should be monitored and evaluated for symptoms (eg, dyspnea, cough or pyrexia) and treated symptomatically, including interruption of the suspected agent as appropriate. Should symptoms develop follow the protocol dose modification guidelines.

Leukostasis

There were isolated cases of leukostasis reported in subjects treated with ibrutinib. A high number of circulating lymphocytes (>400,000/ μ L) may confer increased risk.

Lymphocytosis

Upon initiation of treatment, a reversible increase in lymphocyte counts (i.e., $\geq 50\%$ increase from baseline and an absolute count $5000/\text{mc } \mu\text{L}$), often associated with reduction of lymphadenopathy, has been observed in most subjects with CLL/SLL treated with ibrutinib as a single agent. This effect has also been observed in some subjects with MCL treated with ibrutinib. This observed lymphocytosis is a pharmacodynamic effect and should not be considered progressive disease in the absence of other clinical findings. In both disease types, lymphocytosis typically occurs during the first few weeks of ibrutinib therapy (median time 1.1 weeks) and typically resolves within a median of 8.0 weeks in subjects with MCL and 14 weeks in subjects with CLL/SLL. This pharmacodynamic effect was less prominent or not observed in other indications.

A large increase in the number of circulating lymphocytes (eg, $>400,000/\mu\text{L}$) has been observed in some subjects. Lymphocytosis was not commonly observed in subjects with Waldenström's macroglobulinemia treated with ibrutinib. Lymphocytosis appeared to occur in lower incidence and at lesser magnitude in subjects with CLL/SLL receiving ibrutinib in combination with chemoimmunotherapy.

Hypertension

Hypertension has been commonly reported in subjects treated with ibrutinib. Monitor subjects for new onset of hypertension or hypertension that is not adequately controlled after starting ibrutinib. Adjust existing anti-hypertensive medications and/or initiate anti-hypertensive treatment as appropriate.

Potential for Drug-Drug Interactions: Ibrutinib is primarily metabolized by CYP3A.

Agents That May Increase ibrutinib Plasma Concentrations (CYP3A Inhibitors):

Concomitant use of ibrutinib and drugs that strongly or moderately inhibit CYP3A can increase ibrutinib exposure and strong CYP3A inhibitors should be avoided.

Strong CYP3A inhibitors

Co-administration of ketoconazole, a strong CYP3A inhibitor, in 18 healthy subjects, increased exposure (C_{max} and $\text{AUC}_{0-\text{last}}$) of ibrutinib by 29- and 24-fold, respectively. In a dedicated drug-drug interaction study in patients with B-cell malignancies, co-administration of voriconazole increased C_{max} and AUC by 6.7-fold and 5.7-fold, respectively. In clinical studies, the maximal observed ibrutinib exposure (AUC) was ≤ 2 -fold in 37 patients treated with mild and/or moderate CYP3A inhibitors when compared with the ibrutinib exposure in 76 patients not treated concomitantly with CYP3A inhibitors. Clinical safety data in 66 patients treated with moderate ($n=47$) or strong CYP3A inhibitors ($n=19$) did not reveal meaningful increases in toxicities. Voriconazole and posaconazole can be used concomitantly with ibrutinib as per the dosing guidance described in the specific clinical study protocol. All other strong inhibitors of CYP3A (eg, ketoconazole, indinavir, nelfinavir, ritonavir, saquinavir, clarithromycin, telithromycin, itraconazole, nefazodone and cobicistat) should be avoided, and an alternative with less CYP3A inhibitory potential should be considered. If the benefit outweighs the risk and a strong CYP3A inhibitor must be used, see the recommended dose modifications described in the specific clinical study protocol.

Moderate and mild CYP3A inhibitors

In patients with B-cell malignancies, co-administration of the CYP3A inhibitor erythromycin increased C_{max} and AUC by 3.4-fold and 3.0-fold, respectively. If a moderate CYP3A inhibitor (eg, fluconazole, erythromycin, amprenavir, aprepitant, atazanavir, ciprofloxacin, crizotinib, diltiazem, fosamprenavir, imatinib, verapamil, amiodarone, dronedarone) is indicated in patients with B-cell malignancies, reduce the ibrutinib dose to 280 mg for the duration of the inhibitor use. or as per recommended dose modifications described in the specific clinical study protocol. No ibrutinib dose modifications for moderate inhibitors are required in patients with cGVHD dosed with ibrutinib 420 mg.

No dose adjustment is required in combination with mild inhibitors. Monitor patient closely for toxicity and follow dose modification guidance as needed. Avoid grapefruit and Seville oranges during ibrutinib treatment as these contain moderate inhibitors of CYP3A.

Agents That May Decrease ibrutinib Plasma Concentrations (CYP3A Inducers)

Administration of ibrutinib with strong inducers of CYP3A decreases ibrutinib plasma concentrations by up to 90%. Avoid concomitant use of strong CYP3A inducers (eg, carbamazepine, rifampin, phenytoin and St. John's Wort). Consider alternative agents with less CYP3A induction.

Drugs that may have their plasma concentrations altered by ibrutinib

In vitro studies indicated that ibrutinib is a weak reversible inhibitor toward CYP2B6, CYP2C8, CYP2C9, CYP2C19, CYP2D6, and CYP3A4/5 and does not display time--dependent CYP inhibition. The dihydrodiol metabolite of ibrutinib is a weak inhibitor toward CYP2B6, CYP2C8, CYP2C9, and CYP2D6. Both ibrutinib and the dihydrodiol metabolite are at most weak inducers of CYP isoenzymes in vitro. Therefore, it is unlikely that ibrutinib has any clinically relevant drug-drug interactions with drugs that may be metabolized by the CYP enzymes.

In vitro studies indicated that ibrutinib is not a substrate of P-gp, nor other major transporters, except OCT2. The dihydrodiol metabolite and other metabolites are P--gp substrates. Ibrutinib is a mild inhibitor of P--gp and breast cancer resistance protein (BCRP). Ibrutinib is not expected to have systemic drug-drug interactions with P--gp substrates. However, it cannot be excluded that ibrutinib could inhibit intestinal P--gp and BCRP after a therapeutic dose. There are no clinical data available. To minimize the potential for an interaction in the GI tract, narrow therapeutic range P--gp or BCRP substrates such as digoxin or methotrexate should be taken at least 6 hours before or after ibrutinib. Ibrutinib may also inhibit BCRP systemically and increase the exposure of drugs that undergo BCRP -mediated hepatic efflux, such as rosuvastatin.

Contraindications:

Ibrutinib is contraindicated in subjects with clinically significant hypersensitivity to any of the compound's structural components. Ibrutinib has not been used in subjects with biliary obstruction, acute hepatitis, severe liver failure, or severely impaired renal function; hence, avoid use of ibrutinib in patients with these conditions.

11.2.2 Risks related to blood draws: No major risks are involved with blood draws. Minor complications including bleeding, pain, and hematoma formation at the site of blood draws, vasovagal reactions or infections may rarely occur.

11.2.3 Risks related to CT Scan: CT (computed tomography), sometimes called CAT scan, uses special x-ray equipment to obtain image data from different angles around the body and then uses computer processing of the information to show a cross-section of body tissues and organs. Oral and/or intravenous contrast agents will be used and are usually well tolerated. However, some subjects will experience allergic reactions to intravenous contrast. To lower the risk of allergic reactions, low allergenic contrast agents are administered at NIH clinical center. In addition, subjects will be advised that approximately 2-7% of patients who receive contrast agents will experience a temporary reduction in kidney function lasting up to 2 weeks following infusion and that in rare instances, permanent renal damage can result from the use of the IV contrasting agent. Therefore, in subjects with impaired kidney function, we will not use intravenous contrast.

The amount of radiation subjects will receive from the research scans in this study is 1.3 rem of radiation annually, which is below the guideline of 5 rem (or 0.5 rem in children) per year allowed for research subjects by the NIH Radiation Safety Committee. All female subjects will receive pregnancy testing prior to radiation exposure.

11.2.4 Related to pregnancy and nursing mothers: There are no clinical studies in pregnant women, and it is unknown whether ibrutinib or its metabolites are excreted in human milk. Men and women of child-bearing potential must use highly effective contraceptive (eg, condoms, implants, injectables, combined oral contraceptives, some intrauterine devices [IUDs], sexual abstinence, or sterilized partner) protection while on study and for 90 days after the last dose of study drug. If a female subject or the partner of a male subject becomes pregnant, the sponsor must be notified. Male subjects should refrain from sperm donation.

11.2.5 Related to central line placement (only when indicated): A catheter may be placed in a large vein of the neck, chest, or arm using local anesthetic. Patients will sign a separate consent for the placement procedure. Only trained experienced staff will place the line in order to minimize these procedure related risks. The risks from the procedure are low; they include bleeding, bruising, or infection at the site of insertion. Some patient may experience a vasovagal reaction (lightheadedness, or, rarely, fainting due to temporary lowering of blood pressure). Very rarely (less than 1% of the time), the line placement may nick the lung causing it to collapse during line insertion. If the lung collapses, a tube may have to be inserted into the chest and remain in place until the lung re-expands. Because of this risk, patients will have a chest x-ray following the procedure to make sure the line is in the correct place and that the lung is not collapsed. Once placed, the line will remain in place until drug administration is complete.

11.2.6 Risks related to bone marrow biopsy: The anesthetic can cause some temporary stinging and burning. A pulling sensation and discomfort may be felt as the marrow is withdrawn. Although rare, there is a potential for bleeding at the site and local infection. Bleeding can be stopped by applying local pressure, and infection can be treated with antibiotics.

11.2.7 Risks related to transfusions: Some risks with the transfusion with blood and /or blood products include fever or allergic reactions. These risks are uncommon and are usually mild, but on rare occasions may be severe or life threatening. Extremely rare risks include infections with viruses, such as hepatitis or HIV or serious incompatibility reactions.

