5.7.1 Guideline for Use of CYP Inhibiting Drugs

Ibrutinib is metabolized primarily by CYP3A. Avoid co-administration with strong CYP3A or moderate CYP3A inhibitors and consider alternative agents with less CYP3A inhibition.

- If a strong CYP3A inhibitor (eg, ketoconazole, indinavir, nelfinavir, ritonavir, saquinavir, clarithromycin, telithromycin, itraconazole, nefazadone, posaconazole, or cobicistat) must be used, reduce ibrutinib dose to 140 mg or withhold treatment temporarily (for 7 days or less). Subjects should be monitored for signs of ibrutinib toxicity.
- If a moderate CYP3A inhibitor (eg, voriconazole, erythromycin, amprenavir, aprepitant, atazanavir, ciprofloxacin, crizotinib, darunavir/ritonavir, diltiazem, fluconazole, fosamprenavir, imatinib, verapamil, amiodarone, or dronedarone) must be used, reduce ibrutinib to 140 mg (for 840 mg/day dose, reduce to 280 mg) for the duration of the inhibitor use. Avoid grapefruit and Seville oranges during ibrutinib treatment, as these contain moderate inhibitors of CYP3A.
- No dose adjustment is required in combination with mild inhibitors.
- Avoid concomitant use of strong CYP3A inducers (eg, carbamazepine, rifampin, phenytoin, and St. John's Wort). Consider alternative agents with less CYP3A induction.
- A list of common CYP3A inhibitors and inducers is provided in Appendix 3 of the IB. A comprehensive list of inhibitors, inducers, and substrates may be found at <http://medicine.iupui.edu/clinpharm/ddis/main-table/>. This website is continually revised and should be checked frequently for updates.
- For the most comprehensive effect of CYP3A inhibitors or inducers on ibrutinib exposure, please refer to the current version of the IB.

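### For a moderate CYP3A inhibitor, Section 5.7.1 sets ibrutinib at 140 mg, but Section 11.2.1 states 280 mg and offers the protocol's own rule only as an alternative: a minor dosing inconsistency

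*Combined protocol and SAP*

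**What the plan says.** Section 5.1 fixes ibrutinib at 420 mg daily; no arm uses 840 mg.

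Section 5.7.1, in the Treatment Plan, begins with a general instruction: "Avoid co-administration with strong CYP3A or moderate CYP3A inhibitors". If a moderate inhibitor cannot be avoided, the investigator is to "reduce ibrutinib to 140 mg (for 840 mg/day dose, reduce to 280 mg) for the duration of the inhibitor use". If a strong inhibitor cannot be avoided, the dose is 140 mg or ibrutinib is withheld for 7 days or less.

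Section 11.2.1, in the human subject protection chapter, returns to the same drugs. For a moderate inhibitor in patients with B-cell malignancies it says to "reduce the ibrutinib dose to 280 mg for the duration of the inhibitor use", followed by "or as per recommended dose modifications described in the specific clinical study protocol". It adds that cGVHD patients on 420 mg need no change. For a strong inhibitor that must be used, it gives no dose and tells the reader to "see the recommended dose modifications described in the specific clinical study protocol".

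The two sections also differ on voriconazole. The moderate list in 5.7.1 opens with it: "If a moderate CYP3A inhibitor (eg, voriconazole, erythromycin". Section 11.2.1 discusses it under the strong inhibitors, says that it and posaconazole may be used under the study protocol's guidance, and goes on to "All other strong inhibitors of CYP3A" as the ones to avoid.

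**The concern.** A protocol should give one dose for one situation. Here a subject on 420 mg who needs, say, diltiazem or fluconazole gets 140 mg from one section and 280 mg from another. The 280 mg that appears in 5.7.1 does not reconcile them, because it applies only to a starting dose of 840 mg, which this trial does not use.

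A clinician who took the dose from 11.2.1 would give twice the Treatment Plan dose. It would then be unclear how to classify that dose. Section 12.1 defines an overdose by reference to the dose the protocol specifies, and on this point the protocol contains two figures. A monitor checking for deviations would have the same difficulty. What is at stake is individual dosing and its classification, not the trial's inference.

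**Working it through.** **Do the two texts cover the same case?** Section 5.7.1 names 15 moderate inhibitors and 11.2.1 names 13. All 13 are among the 15; voriconazole and darunavir/ritonavir appear only in the 5.7.1 list. The population in 11.2.1 is patients with B-cell malignancies, which includes all CLL and SLL subjects. So the drugs and patients are the same.

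**Size of the difference.**
- 5.7.1 at the study dose: 140 / 420 = 0.33. At the other level it names: 280 / 840 = 0.33. The section is consistent with itself.
- 11.2.1 at the study dose: 280 / 420 = 0.67.
- Ratio of the two instructions: 280 / 140 = 2.

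**What that means for exposure.** This is illustrative. It assumes exposure proportional to dose, whereas Section 2.6.1 says only that exposure rose with dose, with substantial variability between subjects. Relative exposure = (reduced dose / 420) × fold rise in AUC, where 1.0 is the usual exposure at 420 mg. The erythromycin and 2-fold figures come from 11.2.1.

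| Fold rise in AUC | 140 mg | 280 mg |
|---|---|---|
| 3.0 (erythromycin) | 0.333 × 3.0 = 1.00 (as 420 mg) | 0.667 × 3.0 = 2.00 (as 840 mg) |
| 2.0 (maximum seen in 37 patients on mild and/or moderate inhibitors) | 0.333 × 2.0 = 0.67 (as 280 mg) | 0.667 × 2.0 = 1.33 (as 560 mg) |

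The 2-fold figure pools mild with moderate inhibitors, so it is not specific to the moderate class.

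**Comparators from the protocol.**
- Taking ibrutinib with food, which is allowed, about doubles mean exposure (2.6.1).
- In mild hepatic impairment the AUC rises 2.7-fold (2.6.1) and the starting dose is 280 mg (5.4.4), giving 0.667 × 2.7 = 1.80.
- 34 relapsed CLL patients received 840 mg (2.6.2).
- No maximum tolerated dose was reached up to 1400 mg/day (12.1).
- Safety data in 66 patients on moderate or strong inhibitors "did not reveal meaningful increases in toxicities" (11.2.1).

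The 1.33 to 2.00 range at 280 mg is therefore of the same order as exposures the protocol already accepts.

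**Wording of the deferral.** For strong inhibitors 11.2.1 gives no number and simply points to the study protocol. For moderate inhibitors it gives a number first and then the protocol's rule as an alternative, naming no section. Read literally, 280 mg remains permitted. I put no weight on the full stop before the fragment, since it may come from the text extraction.

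**Voriconazole.** Section 5.7.1 gives the figure of 140 mg in both classes, so there are not two reduced doses. The classes are not handled identically, because short withholding is named as an option only for strong inhibitors. With the 5.7-fold AUC rise quoted in 11.2.1, 140 mg gives 0.333 × 5.7 = 1.90.

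**The case against.** The strongest reply is that precedence is clear enough. Dosing rules belong to Section 5. Section 11.2.1 describes risks and sends the reader back to Section 5 for action: to 5.5 for surgery, and to 5.4 for arrhythmia and diarrhea. Its CYP3A text defers to the study protocol three times, and this document is that protocol. It is also evidently programme-wide background, since it mentions mantle cell lymphoma, Waldenström's macroglobulinemia and cGVHD, none of which is studied here. On that reading 280 mg is a general recommendation that gives way to the trial's own 140 mg.

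Most of this stands, and it is why the point is minor. A reader might infer that the protocol leaves the dose undetermined, or that 280 mg is an equally valid second rule. The documents do not support that, because 5.7.1 is the only treatment-plan rule for CYP inhibitors and is internally consistent. What the reply does not remove is an explicit number, addressed to this trial's population and joined to the correct rule by 'or'. The clean deferral used for strong inhibitors shows how the sentence could have read.

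A reader might also see a voriconazole dose conflict or a defect in the Section 4.2 exclusion. Neither follows. The 140 mg figure is common to both classes, 4.2 names no drugs, and 5.7.1 refers to the IB and a website for class lists. Those sources are not available here and may settle the class.

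**Conclusion.** The inconsistency is real and minor: 140 mg against 280 mg for the same 13 drugs at the 420 mg study dose, with 5.7.1 best read as governing. Under dose proportionality, following 11.2.1 would give about 1.33 to 2.00 times usual exposure, against 0.67 to 1.00 under 5.7.1.

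It would go too far to infer that subjects face material harm. The comparators above point to a small effect, and 5.7.1 first asks that these drugs be avoided. Enrolment is at most 32 (27 evaluable plus up to 5); how many would need a moderate inhibitor is not stated and is probably few. One limit on that reassurance is that Section 10.0 describes this as the first trial use of ibrutinib with fludarabine, so the comparators do not come from the combination.

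Nor do the documents show that 280 mg is pharmacologically wrong. The protocol uses 280 mg in mild hepatic impairment at a similar calculated exposure, and at a 2-fold rise 140 mg falls below usual exposure. The finding is that two doses are stated, not which one is right. Sample size, the two-stage decision rules and the analysis are unaffected.

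**What to change.** In Section 11.2.1, delete the 280 mg instruction, the 'or' fragment after it and the cGVHD sentence, and put in their place a cross-reference to Section 5.7.1 for dose modification. That leaves 140 mg as the only rule. If the sponsor intends 280 mg, amend 5.7.1 instead, so that one dose remains.

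Secondary: check voriconazole against the current IB and list it in one class in both 5.7.1 and 11.2.1. The wording of 4.2 need not change.

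The cost is a few sentences. Section 10.6 requires company review and IRB approval of any amendment, so this is best bundled with the next one. Design, sample size and data collection stay as they are.
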